7. DEFINITIONS OF POPULATIONS

Any protocol deviations, including those due to coronavirus disease 2019 (COVID-19) and related restrictions (see Section 8.1.1), will be considered prior to database lock for their importance and taken into consideration when assigning subjects to populations.

7.1. All Subjects Population

The all subjects population will include all subjects who signed the informed consent form and had any study assessment recorded in the database per the protocol.

7.2. Safety Population

The safety population will include all subjects who received at least 1 dose of study treatment (AM1476 or placebo).

7.3. Pharmacokinetic Population

The PK population will include all subjects who received at least 1 dose of active study treatment (AM1476) and have at least 1 valid PK concentration.

8. STATISTICAL METHODOLOGY

8.1. General

Listings will be provided for all data captured in the database, with the exception of medical history. Listings will include all subjects assigned to the all subjects population and include data up to the point of study completion or discontinuation. Subjects are generally considered to have completed the study if they complete the scheduled follow-up visit (rather than early termination visit). Any subject who discontinues the study will be identified accordingly in the listings. Summaries and statistical analyses will include the subjects assigned to the relevant population based on data type.

Analysis Data Model (ADaM) datasets will be prepared using Clinical Data Interchange Standards Consortium (CDISC) ADaM Version 2.1 (or higher if a new version is issued during the study) and CDISC ADaM Implementation Guide Version 1.1 (or higher if a new version is issued during the study). Pinnacle 21 Community Validator Version 3.0.2 (or higher if a new version is issued during the study) will be utilised to ensure compliance with CDISC standards.

For all statistical analyses, the hypothesis testing will be 2-sided and carried out on 0.05 significance level, unless specifically stated otherwise.

Caution should be used when interpreting results from the statistical analyses conducted in this study because the sample size is not based on power calculations.

Where reference is made to 'valid' data, this refers to non-missing data which meet the predetermined criteria (eg, are not flagged for exclusion).

Where reference is made to 'all calculations', this includes, but is not limited to, summary statistics, statistical analyses, baseline derivation, and changes from baseline.

All figures will be produced on linear-linear or discrete-linear scales, as applicable, unless specifically stated otherwise.

8.1.1. Handling of Data Quality Issues Due to Coronavirus Disease 2019 and Related Restrictions

Due to COVID-19 and related restrictions, there is a high risk for impact to data integrity, with the recognised potential for:

- Missed visits, caused by, for example:
 - Subject unable to travel to site due to restrictions, the need to quarantine, or COVID-19 infection
 - o Subject unwilling to go to site due to fear of COVID-19 infection
 - Site postponing subject's visit due to investigator not being available (eg, if they have been dispatched to hospital handling COVID-19 infections)

- Site unable to replenish supply of investigational product
- Incomplete data entry by sites due to limited resources to support study or no access to source documents or to eCRF
- Outstanding source document verification (SDV) due to sponsor or country restrictions on remote SDV, or no or limited access to site(s) for on-site visits
- Unanswered queries

At the time of the reporting of the study results, all protocol deviations due to COVID-19 or related restriction will be assessed for their severity and impact on the analyses. If needed, appropriate statistical methods will be applied as a mitigating action (eg, data might be categorised into 2 analysis groups, with and without COVID-19 and related restrictions impact); however, this will exclude any imputations of the missing values. Any mitigating actions will be agreed with AnaMar AB in advance and identified in the CSR.

8.1.2. Calculation of the Summary Statistics

For continuous data the following rules will be applied:

- Missing values will not be imputed, unless specifically stated otherwise.
- Unrounded data will be used in the calculation of summary statistics.
- In general, as early termination data are not associated with any scheduled timepoint, they will be excluded from all calculations of summary statistics. Exceptions may be made where justified.

For categorical data the following rules will be applied:

- For ordered categorical data (eg, AE severity), all categories between the possible minimum and maximum categories will be included, even if n = 0 for a given category.
- For non-ordered categorical data (eg, race), only those categories for which there is at least 1 subject represented will be included; unless specifically stated otherwise.
- Missing values will not be imputed, unless specifically stated otherwise. A 'missing' category will be included for any parameter for which information is missing. This will ensure that the population size totals are consistent across different parameters.

8.1.3. Triplicate Readings

For vital signs data only, where triplicate readings are taken, the median of triplicate readings will replace the separate individual triplicate readings in all calculations.

For 12-lead ECG data only, where triplicate readings are taken, the mean of triplicate readings will replace the separate individual triplicate readings in all calculations.

In case of incomplete triplicate readings (eg, only 2 out of 3 readings were recorded), the mean and/or medians will be calculated, as appropriate, based on the number of readings available.

8.1.4. Repeat and Unscheduled Readings

For vital signs and 12-lead ECG data only, any predose value recorded in addition to the original value or a postdose value recorded within 15 minutes of the original value will be defined as a repeat value; any postdose value recorded more than 15 minutes after the original value will be defined as an unscheduled value. For all other data types (eg, laboratory parameters), any value recorded in addition to the original value will be defined as an unscheduled value.

The original value will be replaced by the last associated repeat value in all calculations, with the exception of the 12-lead ECG outlier analysis (see Section 8.6.4).

As unscheduled values are not associated with any scheduled timepoint, they will be excluded from all calculations, with the exception of the baseline derivation (see Section 8.1.5) and 12-lead ECG outlier analysis (see Section 8.6.4).

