# 7.2.3. Vital Signs

Supine blood pressure, supine pulse rate, respiratory rate, and oral body temperature will be assessed at the times indicated in the Schedule of Assessments in Appendix 6 for Part A and Appendix 7 for Part B. Vital signs may also be performed at other times if judged to be clinically appropriate or if the ongoing review of the data suggests a more detailed assessment of vital signs is required.

Day 1 predose blood pressure, pulse rate, and respiratory rate will be measured in triplicate at approximately 2-minute intervals. The median value will be used as the baseline value in the data analysis. Oral body temperature will be measured singly. All subsequent measurements will be performed singly and repeated once if outside the relevant clinical reference ranges.

Subjects must be supine for at least 5 minutes before blood pressure and pulse rate measurements.

For orthostatic vital sign measurements, the supine blood pressure and pulse rate will be measured after the subject has been supine for at least 5 minutes. The subject will then stand for at least 2 minutes and the standing blood pressure and pulse rate will be measured.

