| Blood sampling e,f                |                               |                | Day 1: predose, 0.25, 0.5, 1, 1.5, 2, 3, 4, 6, 8, 12, 16 and 24 hours postdose
Days 4, 6, 7, 8, and 9: predose
Day 10: predose, 0.25, 0.5, 1, 1.5, 2, 3, 4, 6, 8, 12, 16, 24, 36 and 48 hours
postdose |  |
| Urine sampling e,f                |                               |                | Day 1: predose (spot collection), 0 to 24 hours postdose
Day 10: 0 to 24 hours postdose  |  |

| Study Procedures  | Screening
(Days -28 to -2) | Day -1                                       | Days 1 to 12   | Follow-up
(7 to 10 days
post-final dose) |
|---|-------------------------------|--|--|--|
| Safety and tolerability:  |                               |  |  |  |
| Adverse event recording   | X                             | Х  | Ongoing  | Х  |
| Prior/concomitant medication
monitoring                                    | X                             | Х  | Ongoing  | Х  |
| Clinical chemistry, haematology, coagulation, and urinalysis                  | X                             | Х  | Days 3 and 7: predose
Day 10: 48 hours postdose   | Х  |
| Blood pressure, pulse rate,
respiratory rate, and oral body
temperature | X                             |  | Day 1: predose, 2, 4, and 8 hours postdose
Days 2, 4, and 7: predose
Day 10: predose, 2, 4, 8, 24, and 48 hours postdose         | х  |
| Orthostatic vital signs   | X                             |  | Day 1: predose, 2, 4, and 8 hours postdose
Days 2, 4, and 7: predose
Day 10: predose, 2, 4, 8, 24, and 48 hours postdose         | X  |
| 12-lead ECG   | X                             |  | Day 1: predose and 4 hours postdose
Days 2, 4, and 7: predose and 4 hours postdose
Day 10: predose, 4, 24, and 48 hours postdose | X  |
| C-SSRS  | X                             | Х  | Day 12   | Х  |
| Neurological examination  | X                             | a
10 - 10 - 10 - 10 - 10 - 10 - 10 - 10 - | Days 3, 6, 9, and 12 g  | X  |
| Physical examination  | X h                | X i                               | Prior to discharge on Day 12 i  | X i                                 |

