8.6.3. Vital Signs Parameters

For systolic and diastolic blood pressure and pulse rate, orthostatic parameters will be calculated as the supine value (recorded prior to the standing value) subtracted from the standing value. If the time between the supine and standing values used for derivation of the orthostatic value is <2 min, this orthostatic value will be flagged and excluded from all calculations.

All vital signs parameters and their changes from baseline will be listed, as applicable; any value outside the clinical reference range will be flagged. This will include any instances of orthostatic systolic blood pressure <-20 mmHg, orthostatic diastolic blood pressure <-10 mmHg, and orthostatic pulse rate >30 beats/min.

Summary tables and boxplots by treatment and timepoint will be provided for all vital signs parameters and their changes from baseline, as applicable.

8.6.4. 12-lead Electrocardiogram Parameters

All 12-lead ECG parameters and their changes from baseline will be listed; any value outside the clinical reference range will be flagged.

Summary tables and boxplots by treatment and timepoint will be provided for all 12-lead ECG parameters and their changes from baseline.

An outlier analysis will be performed for QT interval corrected for heart rate using Bazett's formula (QTcB) and QT interval corrected for heart rate using Fridericia's formula (QTcF). The analysis will include all individual original, repeat, and unscheduled postdose values.

The maximum postdose values will be summarised by treatment according to the following categories:

● ≤450 ms

- >450 and \leq 480 ms (all instances flagged in the listing)
- >480 and \leq 500 ms (all instances flagged in the listing)
- >500 ms (all instances flagged in the listing)

The maximum increases from baseline will be summarised by treatment according to the following categories:

- ≤30 ms
- >30 and ≤ 60 ms (all instances flagged in the listing)
- >60 ms (all instances flagged in the listing)

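### Only out-of-range vital signs are repeated, and a prompt repeat replaces the original in SAP summaries: a small pull towards the reference range, with no by-treatment count of exceedances

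*SAP*

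**What the plan says.** - Protocol 7.2.3 takes Day 1 predose blood pressure, pulse rate and respiratory rate in triplicate, whatever the values, and uses the median as baseline. After that: "All subsequent measurements will be performed singly and repeated once if outside the relevant clinical reference ranges". In-range readings are not repeated, and no time is set for the repeat.
- SAP 8.1.4 defines a repeat as "any predose value recorded in addition to the original value or a postdose value recorded within 15 minutes of the original value". A later post-dose value is unscheduled and left out of calculations, so the original then stands.
- SAP 8.1.4 continues: "The original value will be replaced by the last associated repeat value in all calculations". The only exception is the 12-lead ECG outlier analysis. SAP 8.1 explains that the phrase on calculations has wide scope: "this includes, but is not limited to, summary statistics, statistical analyses, baseline derivation, and changes from baseline".
- SAP 8.6.3 uses these values: "Summary tables and boxplots by treatment and timepoint will be provided for all vital signs parameters and their changes from baseline". For listings, "any value outside the clinical reference range will be flagged". No by-treatment count of out-of-range vital signs is planned.
- The Part B schedule (Protocol Appendix 7) has single predose readings that follow earlier doses: "Days 2, 4, and 7: predose" and "Day 10: predose, 2, 4, 8, 24, and 48 hours postdose". On its plain wording the predose clause of SAP 8.1.4 covers them.
- SAP 8.6.4 builds its QTc categories from original, repeat and unscheduled values together.

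**The concern.** A rule that re-measures only extreme readings and keeps the second value invites regression to the mean. The expected repeat lies below a high original and above a low one, so on average the analysed values move inwards. Because baseline is a triplicate median taken regardless of value, change from baseline is affected mainly on the post-dose side. If the drug pushes readings out of range, the difference from placebo is somewhat understated and the tails of the boxplots are trimmed.

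Vital signs are a primary safety endpoint (Protocol 2.2.1). An exceedance that returns to normal within 15 minutes leaves every by-treatment vital-sign display and is found only by reading listings. The SAP did not accept that for QTc.

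**Working it through.** The plan states no figure on this point, so there is none to reproduce. The size below is illustrative.

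**Inputs.** Systolic pressure; upper limit 140 mmHg, borrowed from exclusion criterion 6 in Protocol 4.2. Assumed: lower limit 90, placebo mean 120, and between/within-subject SDs of 9/6, 8/8 or 8/10 mmHg. Group sizes are 6 active and 12 pooled placebo (six Part A groups with 2 each; pooling per SAP Table 1).

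**Model.** The original is subject mean plus error, with variance s² = between² + within². With error correlation ρ between original and repeat, the slope of repeat on original is c = (between² + ρ·within²)/s². If a share p of repeats falls within 15 minutes, the bias of an arm with mean μ is

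p·(c − 1)·s·[φ((140 − μ)/s) − φ((90 − μ)/s)].

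**One case in full** (8/8, ρ = 0, p = 1): s = √128 = 11.31 and c = 64/128 = 0.5.
- Placebo, μ = 120: −0.5 × 11.31 × (0.0836 − 0.0119) = −0.41.
- Active, μ = 130: −0.5 × 11.31 × (0.2699 − 0.0008) = −1.52.
- Difference shown: 10 − 1.52 + 0.41 = 8.88.

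**A true +10 mmHg difference is shown as:**

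| Setting | 9/6 | 8/8 | 8/10 |
|---|---|---|---|
| ρ = 0, all repeats within 15 min (upper case) | 9.35 | 8.88 | 8.45 |
| ρ = 0.5, all in time; or ρ = 0, half in time | 9.67 | 9.44 | 9.22 |
| ρ = 0.8, half in time | 9.93 | 9.89 | 9.84 |

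The loss is proportional to p(1 − ρ), which is why the two settings in the middle row agree. A simulation of 2,000,000 subjects per arm agreed with the upper case to within 0.02. A second set of assumptions (total SD 12, correlation 0.6 to 0.9 between the two readings) gives 9.05 to 9.76.

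**Against sampling error.** SE = SD × √(1/6 + 1/12), where the raw SD is s and the change-from-baseline SD is within × √(1 + 0.449); 0.449 is the variance factor for the median of three. This gives 5.4 to 6.4 mmHg raw and 3.6 to 6.0 for change from baseline. The upper-case losses of 0.65, 1.12 and 1.55 mmHg are 0.12 to 0.26 of an SE (0.65/5.41 to 1.55/6.02).

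**Falls.** In the upper case a true fall of 10 is shown as 9.58, 9.19 or 8.56, and a fall of 5 as 4.79, 4.59 or 4.28. For the fall of 5, fewer active than placebo readings trigger a repeat (2.1–5.1% against 3.5–6.9%), so replacement is not always more frequent on active.

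**Tails at +10, active readings above 140:**

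| | 9/6 | 8/8 | 8/10 |
|---|---|---|---|
| Originals | 17.8% | 18.8% | 21.7% |
| After replacement (ρ = 0, p = 1) | 9.6% | 8.0% | 8.5% |
| True subject means | 13.3% | 10.6% | 10.6% |

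**Accuracy of the two rules.** Root-mean-square error of the difference is √(bias² + active variance/6 + placebo variance/12). Simulated at ρ = 0 and p = 1, raw values give 5.13, 5.25 and 5.85 with replacement, against 5.41, 5.66 and 6.40 with originals. Change from baseline gives 3.57, 4.72 and 5.84 against 3.61, 4.82 and 6.02. Replacement was also lower at ρ = 0.5 and 0.8.

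**The case against.** The best defence is that the rule does more good than harm to the summaries. A repeat removes noise as well as signal: in the model above the SAP rule has the lower root-mean-square error for all three SD pairs at all three correlations, and in the upper case its share above 140 is nearer the truth than the originals are. It also guards against artefacts. One reading wrong by 20 mmHg (illustrative) moves a mean of 6 by 20/6 = 3.3 mmHg, more than twice the largest loss found. This stands, and it rules out making originals the main analysis.

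It is also fair that the upper case is pessimistic. With independent errors, the 8/8 and 8/10 pairs imply correlations of only 0.50 and 0.39 between two readings minutes apart. No inferential safety analysis is planned (SAP 8.6.6), originals stay listed and flagged, and escalation rests on Sponsor and Investigator review (Protocol 3.6). The rule is the same in both arms and creates no difference where there is no drug effect. For a predose repeat, that day's dose is a natural bound even though the SAP sets none.

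None of this supplies a by-treatment view of exceedances. A count is a different summary from a mean, and the SAP already treats it so for QTc.

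**Conclusion.** The concern holds in a limited form. Protocol 7.2.3 and SAP 8.1.4 together make replacement depend on the reading, and on average this pulls by-treatment summaries slightly towards the reference range. The direction follows from the rules. The size, a loss of 0.07 to 1.55 mmHg from a true +10, rests on assumed SDs, limits, correlations and repeat timing.

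Three stronger readings might be inferred, and the documents do not support them:

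- **That the rule hides exceedances altogether.** All captured values are listed and out-of-range ones flagged; what is missing is a by-treatment count.
- **That every repeat displaces its original.** A post-dose repeat after more than 15 minutes does not, and the share within 15 minutes is unknown.
- **That the main summaries should use originals.** That would remove a small bias and restore more noise.

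This is a minor point with a cheap improvement, and it does not call into question the planned means or boxplots.

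**What to change.** 1. SAP 8.1.4: extend the exception from replacement, now given only to the ECG outlier analysis, to a vital-signs outlier summary. Leave the rule for the main summaries as it is.
2. SAP 8.6.3: add a by-treatment table of subjects with any out-of-range vital sign after the first dose, including the Part B predose readings on Days 2, 4, 7 and 10. Use original, repeat and unscheduled values, as 8.6.4 does for QTc, and the reference ranges already used for the listing flags. Count separately the subjects still out of range on repeat.
3. Optional: show the vital-sign summaries with original readings as a sensitivity display.

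The cost is SAP wording, one table shell and its programming. No new data are needed and clinical conduct does not change. The downside is that single readings over-count exceedance in both arms, so the table must be read against placebo; the still-out-of-range count helps with that.

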8.1.5. Definitions of Baseline and Change from Baseline

The baseline will be defined as the last value recorded prior to the first dose. If the date/time of the value is incomplete or missing, it will be excluded from the baseline calculation, unless the incomplete date/time indicates the value was recorded prior to the first dose.

Individual changes from baseline will be calculated by subtracting the individual subject's baseline value from the value at the postdose timepoint.

The summary statistics for change from baseline will be derived from individual subjects' values (eg, mean change from baseline will be the mean of the individual changes from baseline for all subjects, rather than difference between the mean value at the postdose timepoint and mean value at baseline).

See Section 8.1.4 for more detail on handling repeat and unscheduled readings in the calculations. See Section 8.1.3 for more detail on handling of triplicate readings in the calculations.

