#### Group A3

It is planned for each subject in Group A3 to have the same treatment in both treatment period such that each subject will receive 2 single doses of AM1476 or placebo during the study. On Day 1 in Treatment Period 1, doses will be administered in the fasted state in accordance with a randomisation schedule. On Day 1 in Treatment Period 2, doses will be given 30 minutes after starting a standard high-fat breakfast. Although a food-effect evaluation is planned to occur in Group A3, this may be subject to change depending upon ongoing review of the PK data.

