## Schedule of Assessments - Part A (Single Dose)

| Study Procedures  | Screening 
(Days -28 to -2) |        | Follow-up  |                            |
|---|--|--------|--|----------------------------|
|   |  | Day -1 | Days 1 to 3  | (7 to 10 days
postdose) |
| Clinical chemistry, haematology, coagulation, and urinalysis                  | X  | Х      | 48 hours postdose                                  | X                          |
| Blood pressure, pulse rate,
respiratory rate, and oral body
temperature | х  |        | Predose and 1, 2, 4, 8, 24, and 48 hours postdose  | х                          |
| Orthostatic vital signs   | X  |        | Predose and 1, 2, 4, 8, 24, and 48 hours postdose  | X                          |
| 12-lead ECG   | X  |        | Predose, and 1, 4, 8, 12, 24 and 48 hours postdose | X                          |
| Telemetry   |  |        | From at least -1 hour predose to 24 hours postdose |                            |
|   |  |        |  |                            |
| Neurological examination  | X  |        | Days 1 (postdose) and 3 i               | X                          |
| Physical examination  | X j                             | Xk     | Prior to discharge on Day 3 k           | X k             |

Abbreviations: CYP = cytochrome P450; ECG = electrocardiogram; FSH = follicle-stimulating hormone; PK = pharmacokinetic(s); PM = poor metaboliser(s); TMF = Trial Master File.

a. Interim medical history.

b. Performed in serum at Screening and in urine at all other times. A positive urine pregnancy test will be confirmed with a serum pregnancy test.

c. Height measured at Screening only.

f. Timepoints may be changed based on emerging data. Any changes to the scheduled times of PK assessments will be agreed with the Sponsor and documented in the TMF.

i. Symptom-directed neurological examination(s) will be performed on Day 1 and Day 3.

j. Full physical examination

k. Symptom-directed physical examination(s).

1. Group A1 screening period to be from Days -35 to -2.

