1. INTRODUCTION

This SAP has been developed after review of the clinical study protocol (Final Version 5 dated 06 January 2021) and electronic case report form (eCRF).

This SAP describes the planned analysis of the pharmacokinetic (PK), safety, and tolerability data from this study. A detailed description of the planned TFLs to be presented in the clinical study report (CSR) is provided in the accompanying TFL shells document.

In general, the analyses are based on information from the protocol, unless they have been modified by agreement with AnaMar AB. A limited amount of information about this study (eg, objectives, study design) is given to help the reader's interpretation.

This SAP must be finalised prior to any unblinding of study data for analysis purposes (interim or final). Additionally, the SAP and TFL shells should be finalised prior to any programming activities commencing.

This SAP supersedes any statistical considerations identified in the protocol; where considerations are substantially different, they will be so identified. If additional analyses are required to supplement the planned analyses described in this SAP, they may be performed and will be identified accordingly in the CSR. Any substantial deviations from this SAP will be agreed with AnaMar AB and identified in the CSR.

This SAP is written with consideration of the recommendations outlined in the International Conference on Harmonisation (ICH) E3 guideline *Structure and Content of Clinical Study Reports*, ICH E8 guideline *General Considerations for Clinical Trials*, and ICH E9 guideline *Statistical Principles for Clinical Trials*.^{1,2,3}

The document history is presented in Appendix 1.

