8.6. Safety and Tolerability Assessments

8.6.1. Adverse Events

All AEs will be coded using the Medical Dictionary for Regulatory Activities (MedDRA) Version 23.1 (or higher if a new version is issued during the study; see the DMP for more details).

A treatment-emergent adverse event (TEAE) will be defined as an AE that starts during or after the first dose, or starts prior to the first dose and increases in severity after the first dose.

A treatment-related TEAE will be defined as a TEAE with a relationship of possibly related or related to the study treatment, as determined by the investigator.

All AEs will be listed. In addition to the data recorded in the database, the listings will include derived onset time and duration. Onset time will be calculated from the time of the last associated dose for TEAEs only. Where the last associated dose is referring to the last dose received prior to the start of a TEAE.

The frequency of subjects with TEAEs and the number of TEAEs will be summarised for the following categories:

- TEAEs (overall, serious, leading to discontinuation, and leading to death) by treatment
- TEAEs by severity and treatment
- Treatment-related TEAEs (overall, serious, leading to discontinuation, and leading to death) by treatment
- Treatment-related TEAEs by severity and treatment

The frequency of subjects will be summarised separately for TEAEs and treatment-related TEAEs by the following:

- System organ class, preferred term, and treatment
- Preferred term and treatment

For the AE data the following rules will apply:

- For the derivation of relationship (applicable to AEs captured on the 'change in the severity' eCRF form only): The relationship to study treatment is not captured on the AE change in severity eCRF form because it is always assumed to be the same as the relationship captured on the first eCRF form completed for this AE (initial severity). Therefore, for these cases the missing relationship will be set to that captured on the first form completed for this AE.
- For the derivation of treatment-emergent status (applicable to all AEs): If the start date/time of an AE is incomplete or missing, an AE will be assumed to not be a TEAE, unless the incomplete start date/time or the end date/time indicates an AE started after the first dose.

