10. SIGNIFICANT CHANGES FROM THE PROTOCOL-SPECIFIED ANALYSES

There were no significant changes from the protocol-specified analyses.

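### SAP 8.1.5 sets a single baseline with no rule by treatment period, so as written Group A3's fed-period vital-sign and ECG changes are measured from a Period 1 value

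*SAP*

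**What the plan says.** SAP 8.1.5 defines baseline once for all data: "The baseline will be defined as the last value recorded prior to the first dose". Change is the postdose value minus that subject's baseline. The sections on triplicates (8.1.3), repeat and unscheduled readings (8.1.4), vital signs (8.6.3) and ECG (8.6.4) add nothing by treatment period.

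Group A3 receives two single doses, fasted in Period 1 and fed in Period 2, with at least 6 days between periods (SAP 4.1). Protocol 3.1.1 says of the second: "On Day 1 in Treatment Period 2, doses will be given 30 minutes after starting a standard high-fat breakfast". SAP 6, Table 1 gives A3 fed its own treatment column and pools placebo over groups and dietary states.

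Vital-sign and ECG changes are listed and summarised by treatment and timepoint. For QTcB and QTcF, SAP 8.6.4 adds: "The maximum increases from baseline will be summarised by treatment according to the following categories". The categories are up to 30 ms, above 30 to 60 ms, and above 60 ms.

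The Part A schedule (Protocol Appendix 6) applies to Period 2 of Group A3 as well. It sets ECGs at "Predose, and 1, 4, 8, 12, 24 and 48 hours postdose" and vital signs predose and at 1, 2, 4, 8, 24 and 48 hours. Protocol 7.2.3 has blood pressure, pulse rate and respiratory rate taken in triplicate before dosing on Day 1, and says: "The median value will be used as the baseline value in the data analysis". It does not say which period's Day 1.

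**The concern.** For a subject dosed in two periods, the first dose is the Period 1 dose. The Period 2 predose reading comes after it and so cannot be the baseline under the text. Each fed-period change is then a Period 2 value minus a Period 1 value, and anything that moved between the periods is counted as part of the change after the fed dose. Within the fed change columns it cannot be told apart from an effect of the drug given with food.

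Vital signs and ECG parameters are primary safety endpoints (SAP 3.1), and descriptive summaries are the only safety analysis planned (SAP 8.6.6). The definition behind those summaries should therefore be clear. The same rule would apply to any of Groups A7 to A9 that include a food-effect period.

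**Working it through.** **What the rule does.** For one A3 subject, let B1 and B2 be the predose values in Periods 1 and 2, and F a fed postdose value.

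- Change under SAP 8.1.5: F − B1 = (F − B2) + (B2 − B1).
- Change from a same-period baseline: F − B2.

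The difference is B2 − B1, which enters every fed change one-for-one. A QTc increase is classed as above 30 ms when (F − B2) + (B2 − B1) > 30, and likewise for 60. A shift in either direction can therefore move a subject across a boundary.

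**How much output is touched.**

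- Fed active column: 6 subjects at 6 postdose times on Days 1 to 3 for vital signs (1, 2, 4, 8, 24, 48 h) and 6 for ECG (1, 4, 8, 12, 24, 48 h). Every change in the column is affected. Follow-up is not counted.
- Pooled Part A placebo: 6 groups × 2 = 12 subjects. If both A3 periods are counted in by-timepoint tables, there are 12 + 2 = 14 records per timepoint, of which 2 are fed-period. The SAP does not say how these are counted.
- QTc maximum-increase table, with one maximum per placebo subject: 2/12 = 16.7% have a maximum that can come from the fed period.

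**Effect on spread.** The documents give no variances or correlations, so what follows is assumption. Take equal variance at all readings, correlation ρw between readings in the same period and ρa between readings in different periods.

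- SD of the fed change, Period 1 baseline relative to same-period baseline: √[(1 − ρa)/(1 − ρw)].
- SD of the contrast (fed change minus fasted change), common baseline relative to per-period baselines. With a common baseline, B1 cancels and the variance is 2σ²(1 − ρa). With per-period baselines it is 4σ²(1 − ρw). The ratio is √[(1 − ρa)/(2(1 − ρw))].

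| ρw / ρa | Fed change | Fed-minus-fasted contrast |
|---|---|---|
| 0.85 / 0.60 | √(0.40/0.15) = 1.63 | √(0.40/0.30) = 1.15 |
| 0.80 / 0.70 | √(0.30/0.20) = 1.22 | √(0.30/0.40) = 0.87 |
| 0.75 / 0.70 | √(0.30/0.25) = 1.10 | √(0.30/0.50) = 0.77 |
| 0.70 / 0.70 | √(0.30/0.30) = 1.00 | √(0.30/0.60) = 0.71 |

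The fed change columns are between no noisier and about 1.6 times noisier. For the contrast, the common baseline is more precise in three of the four cases. These ratios concern precision only. A systematic shift between periods stays in the contrast under a common baseline.

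Equal variance is doubtful for blood pressure, pulse rate and respiratory rate, because the Day 1 predose value is a triplicate median and later readings are single. It is more plausible for ECG, where all scheduled readings are triplicate means.

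**The case against.** A single pre-treatment baseline is a defensible choice. It is the only A3 value certain to be free of drug, and it cancels when fed and fasted are compared within subject. The fixed fasted-then-fed order mixes food with period to some degree whatever baseline is used. The Period 2 predose reading has its own weakness: the documents do not say whether it is taken before the breakfast that starts 30 minutes before dosing. Absolute values are listed and summarised, so a reader could see a predose shift and recompute the changes. The table shells are not among the documents and might set a baseline by period.

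All of that stands, and it limits the weight of the point. It does not settle what the SAP says: the SAP is where baseline is defined, and it gives no reason for using a Period 1 value in Period 2.

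A reader might infer two stronger things:

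- **That the SAP contradicts the protocol.** Since the SAP says "This SAP supersedes any statistical considerations identified in the protocol" and its section 10 says "There were no significant changes from the protocol-specified analyses", that statement would then be wrong. But Protocol 7.2.3 names no period, and for A3 the Day 1 predose median of Period 1 satisfies both documents. A conflict arises only if the protocol means each period's Day 1, which it does not say.
- **That the wording on adverse-event onset fixes the meaning of first dose.** SAP 8.6.1 uses a different term there: "Where the last associated dose is referring to the last dose received prior to the start of a TEAE". That term is needed for Part B's repeated doses in any case, and shows little about what the baseline section intends.

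**Conclusion.** The gap is real and minor. As written, the fed-period vital-sign and ECG changes in Group A3, the fed column of the QTc maximum-increase table, and the A3 placebo subjects' fed-period share of pooled placebo all use a baseline at least about 6 days old, while a Period 2 predose reading is scheduled.

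The scope is descriptive change-from-baseline output for one planned group of 8, of whom 6 are active. Absolute values, the absolute QTc categories, the laboratory summaries (SAP 8.6.2 plans no change from baseline) and the PK food-effect model (SAP 8.5.3.2) do not depend on it. The size is unknown: the ratios above rest on assumed correlations and include no effect.

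A reader might also conclude that the fed-versus-fasted safety comparison is less precise because of the rule. The documents do not support that, because the common baseline cancels in the contrast. The problem lies in the fed change columns themselves. The conclusion rests on reading first dose as the first dose in the study, which is the plain sense of the text, and on the unseen table shells not saying otherwise.

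**What to change.** Leave the existing rule as it is for Period 1 and for all single-period groups, so that A3 fasted stays on the same footing as A1, A2 and A4 to A6. Add to SAP 8.1.5:

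*For Treatment Period 2 of food-effect groups, baseline is the last value recorded before the Period 2 dose and after check-in (Day -1) for that period; if there is none, change from baseline for that period is not calculated.*

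The check-in limit stops a postdose reading from Period 1 serving as the Period 2 baseline. Keep changes from the Period 1 baseline as a supportive listing in case of carryover. State whether the Period 2 predose reading is taken before the high-fat breakfast; without that, the wording alone does not put the fed and fasted baselines under the same conditions. If a single baseline is what the sponsor intends, the SAP should say so and give the reason.

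The cost is a sentence and one extra listing, with no new assessments. The downside is that a Period 2 baseline relies on the washout being adequate. Protocol 3.4 judges the 6-day interval sufficient on non-clinical data.
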